D.3.4 Acute Phase Monitoring, both arms: Patients will be fitted with an esophageal manometry catheter, will undergo diaphragm ultrasound measurements, and will be connected to RIP bands during SBTs. Volumetric capnography with an airway flow sensor will be placed at the end of the endotracheal tube to measure Carbon dioxide concentration, tidal volume, and airway pressures.

Once the patient passes the oxygenation test, an airway occlusion maneuver will be performed to measure neuromuscular strength, followed by a SBT. Daily SBTs are required and will be performed between 9 and 11 AM on CPAP of 5 cmH₂O. The primary study outcome (length of the weaning phase) is defined as the time from initiation of the first SBT until successful passing of an SBT (or extubation, whichever comes first). We will use validated objective criteria to define successful passing of the SBT, and track delays in extubation (> 6 hr between SBT passing and extubation). These criteria are based on our previous publications and are detailed in the description of the primary outcome above, and again below.^{16, 75} Patients who fail the initial SBT will move on to the weaning phase, and will undergo the weaning phase randomization to allocate treatment or control arms for weaning management.

D.3.5 Spontaneous Breathing Trials and success/failure

Variable	Failure within 2 hours
pH (arterial or capillary)	< 7.32
End tidal CO ₂	↑10 mmHg from baseline
Oxygenation	FiO ₂ > 0.5 and SpO ₂ < 90% on PEEP = 5 cmH ₂ O
HR	↑ > 40 BPM over baseline
Rapid Shallow Breathing Pattern (RSBI) (bpm/ml/kg)	≥ 12

Pressure.Rate.Product (PRP)	>500
Retractions	Moderate or Severe Retractions

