Respiratory load (resistance and compliance), effort (PRP, PTP) and combination measures of capacity, load or effort (TTI, Diaphragm Contractile Activity, Phase Angle) will be measured daily during or just before SBTs, as detailed in the data collection table. Analysis of each of these measures against the primary outcome will mimic what is presented above for aPiMax and Diaphragm thickness, with correlation for continuous variables, as well as categorization into distinct ranges for ANOVA.

Secondary Outcomes, SBT failure: In addition to weaning duration, we will also examine whether the respiratory measures in the data collection table taken just prior to or during each SBT are associated with the patient passing the SBT. For example with aPiMax and ePiMax, we will examine if there is a dose response relationship between PiMax measured just before the SBT and the rate of passage of the subsequent SBT (e.g., similar to Figure 3). In addition, we will compare mean or median values for aPiMax between patients who pass versus fail the SBT using a t-test or MWU test. Finally, we will examine aPiMax as a continuous variable to determine its ability to discriminate passage of the subsequent SBT using the Area Under the Curve (AUC) of the Receiver operating Characteristic Plot (ROC). Similar analysis will be done for all other respiratory measures in Table 2, and we will compare the AUCs (using a Chi-squared test) for each individual respiratory parameter against the others to identify which of these tests have the highest sensitivity, specificity, and overall discrimination of SBT failure. We will subsequently generate multivariate logistic regression models to identify which combination of these measures of capacity, architecture, load, and effort

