retain an independent association with SBT failure. Because SBTs will be repeated daily, we will use a hierarchical logistic regression model to control for repeated measures from each patient as well as controlling for the other potential confounding variables detailed in the data collection table. We anticipate that 240 patients will undergo SBT testing, and 90% of these patients will pass the SBT within 28 days of the weaning phase randomization. As such, we would be able to include at least 20 variables in a multivariable hierarchical logistic regression model. Finally, we will determine whether common “phenotypes” for weaning failure can be determined. We anticipate four possible phenotypes by combining information from all available measures of capacity, load, effort, and architecture. Based on our preliminary data, we anticipate that patients with high load will be more likely to fail weaning, but that this effect will be more pronounced if they have diminished respiratory muscle capacity. We hypothesize that the rates of passage of the SBT will increase incrementally from phenotype 1 to 4: (1) Diminished capacity, high load and effort; (2) Normal capacity, high load and effort; (3) Diminished capacity, low load and effort; (4) Normal capacity, low load and effort. These phenotypes are exploratory; thus, no power analysis is provided.

D.6.4.3 SA3 Analysis Plan: To determine if patient effort of breathing during both acute and weaning phases of MV is independently associated with the development of respiratory muscle weakness.

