The analytic approach for secondary aims and outcomes such as mortality and ventilator free days will follow those described above. For categorical data, a χ^2 or Fisher's exact test will be used to compare difference between groups. Logistic regression will be used to assess binary outcomes, and a multinomial/ordinal logistic regression will be used for categorical outcomes (> 2 categories) while adjusting for covariates. To assess the association between 2 continuous variables, a Pearson or Spearman correlation will be used, and analysis of covariance (ANCOVA) will be used to adjust for covariates. Generalized Estimating Equations (GEE) or mixed effect models will be used when necessary to analyze repeated measures. Because of the physiologic nature of the study with a Phase II design,

multiple comparisons adjustment is not planned for secondary outcomes. Analyses will be performed using the appropriate recent version of the SAS statistical software (SAS Institute Inc., Cary, NC).

In order to increase precision around the effect estimates for the primary and secondary aims and to reflect the stratified sampling, all analyses are adjusted for block randomization variables.³ For acute phase these are age group (infant, child, and adolescent) and whether or not the subject was immunocompromised. For the weaning phase this is acute phase randomization grouping and age group. In addition, variables thought to be potential confounders on the relationship between intervention and outcome with large differences between groups (standardized effect sizes as detailed above) will also be included in all adjusted analyses. Unadjusted analyses will be presented to summarize data; all primary and secondary outcomes will present adjusted analyses controlling for age category, immunosuppression and imbalanced baseline variables. Potential confounders will be assessed for multicollinearity and if present, the confounder with the highest biological plausibility to impact the effect of the intervention on the outcome will be selected for inclusion as a model covariate.

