Model assumptions and fit for multiple linear regression (with or without log transformation) will be assessed visually for normality of residuals as well as variance inflation factor and difference in betas (DFBETAS) for influential points. Model fit for binary multiple logistic regression will be assessed with Pearson Chi-square and deviance. Firth's penalized likelihood method will be used in subgroup analyses when event rates are small to reduce bias in the parameter estimates.⁴ When using negative binomial regression, model fit will be assessed for over and underdispersion with the scaled Pearson Chi-square/deviance and influential points assessed as previously described. The proportional hazards assumption will be assessed when using Cox proportional hazards modeling using graphical approaches ("log-log" figures and Kaplan-Meier curves) for each covariate. Repeated measures analysis for ventilator settings, lung mechanics, and respiratory measures will be assessed with linear mixed models and generalized linear mixed models that include a variable for time from randomization to control for correlation of values within each patient using the first-order autoregressive structure. The robust sandwich estimators for standard errors will be used to reduce heteroscedasticity when appropriate.

A detailed outline of each outcome's analysis approach to control for blocking variables and confounders is given in the Table 1. Pre-specified comparisons of interest are REDvent acute vs. usual care acute, REDvent weaning vs. usual care weaning, and four group combination: 1) REDvent acute + REDvent weaning 2) REDvent acute + usual care weaning 3) Usual care acute + usual care weaning 4) usual care acute + REDvent weaning. The four group combinations comparisons are exploratory and will only be considered if there are noted differences between both acute and weaning phase interventions.

October 2019- new milestone accrual plan

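### For SBT failure, the pass/fail tests and AUC comparisons name neither the SBTs per child that enter nor a clustered variance, although SBTs repeat daily

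*Combined protocol and SAP*

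**What the plan says.** Protocol D.6.4.2, under the SBT-failure secondary outcomes (same text in both protocol versions), asks whether respiratory measures "taken just prior to or during each SBT are associated with the patient passing the SBT". Section D.3.4 states "Daily SBTs are required". The univariable steps are:

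- to "compare mean or median values for aPiMax between patients who pass versus fail the SBT using a t-test or MWU test";
- a ROC AUC for aPiMax, and likewise for the other respiratory measures;
- a ranking step: "we will compare the AUCs (using a Chi-squared test) for each individual respiratory parameter against the others".

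No clustered method is attached to any of these, and the text does not say which SBT or SBTs of a child are used.

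The multivariable step that follows is treated differently: "Because SBTs will be repeated daily, we will use a hierarchical logistic regression model to control for repeated measures from each patient".

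The final SAP (July 2024) adds a general rule, "Generalized Estimating Equations (GEE) or mixed effect models will be used when necessary to analyze repeated measures", which is also in the Fall 2019 SAP. It adds a more specific one: "Repeated measures analysis for ventilator settings, lung mechanics, and respiratory measures will be assessed with linear mixed models and generalized linear mixed models". Tables 1 and 2 of the final SAP contain no entry for the AUC analyses, so D.6.4.2 remains their only specification.

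**The concern.** A child who fails on several days supplies several failed-SBT records with correlated measurements, and usually a passed one as well. An unpaired t-test or Mann-Whitney test, an ordinary AUC standard error and the usual chi-squared comparison of AUCs all assume independent records. The usual AUC comparison allows for two measures being read on the same SBT, but not for several SBTs coming from one child.

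The AUC comparison is the step by which the plan decides which bedside measure best discriminates SBT failure. If its variance is wrong, one measure may be declared better than another on too little evidence, and the result could rest on the few slowest-weaning children.

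**Working it through.** The plan states no power or error rate for these tests, so there is no figure to reproduce. The check asks whether clustering would occur, in which direction it acts, and by how much.

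**Inputs from the documents.** 240 children undergo SBT testing and 90% pass within 28 days (D.6.4.2). About 25% of intervention patients in the pilot passed the first SBT (D.6.4.1), applied here to all children. Weaning lasts 2.2 to 4 days (D.6.4.1), a rough guide to the number of failed SBTs. Two-sided alpha 0.05 is stated for the primary outcome and assumed here.

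**Overlap.** Children who pass at some point: 240 × 0.90 = 216. Children who fail the first SBT: 240 × 0.75 = 180. Children who do both: 216 + 180 − 240 = 156. Pass and fail are therefore not separate groups of patients unless one SBT per child is chosen.

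**Variance of the pooled mean difference.** Let child *i* have *m* failed SBTs and pass indicator *p*, with P passes, F failed SBTs and within-child correlation ρ. In units of the measurement variance:

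- naive = 1/P + 1/F
- true = 1/P + [F + ρ Σm(m−1)]/F² − 2ρ Σ(mp)/(PF)
- type I error = 2[1 − Φ(1.96 ÷ (true SE/naive SE))]

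The second term of the true variance inflates it. The third, from the correlation between a child's own failed and passed SBTs, reduces it.

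**Assumptions not in the documents.** ρ from 0.3 to 0.7. Failed SBTs among later passers are geometric with mean 1.5 to 4, so that E[m(m−1)] = 2 × mean × (mean − 1). Each of the 24 never-passers has 5 to 28 failed SBTs.

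**Example** (ρ = 0.5, mean 2.2, 28 failed SBTs per never-passer):

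- F = 156 × 2.2 + 24 × 28 = 1015.2
- Σm(m−1) = 156 × 5.28 + 24 × 28 × 27 = 18,968
- true = 0.00463 + 0.01019 − 0.00157 = 0.01325
- naive = 0.00463 + 0.00099 = 0.00561
- SE ratio = √2.36 = 1.54; type I error 20%

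With 5 failed SBTs per never-passer instead, true = 0.00640, naive = 0.00679, ratio 0.97, type I error 4.3%.

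**True/naive SE ratio (type I error) for ρ = 0.3 to 0.7:**

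| Failed SBTs per never-passer | mean 1.5 | mean 2.2 | mean 4 |
|---|---|---|---|
| no never-passers (all 240 pass) | 0.77–0.91 (1.1–3.1%) | 0.87–0.95 (2.5–3.9%) | 1.00 (5.0%) |
| 5 | 0.98–0.99 (4.5–4.8%) | 0.96–0.98 (4.1–4.6%) | 0.99 (4.8–4.9%) |
| 10 | 1.13–1.28 (8.2–12.5%) | 1.08–1.17 (6.8–9.4%) | 1.03–1.07 (5.7–6.7%) |
| 20 | 1.33–1.67 (14.0–24.0%) | 1.25–1.52 (11.6–19.6%) | 1.14–1.29 (8.4–12.9%) |
| 28 | 1.43–1.86 (17.1–29.1%) | 1.35–1.70 (14.6–25.0%) | 1.21–1.45 (10.6–17.7%) |

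**AUC comparison** (simulation, 1,000 runs per setting, DeLong standard errors, ρ 0.3 to 0.7). With equal daily pass chances apart from the measures, the SE ratio for the AUC difference is 0.97–1.14 and type I error 4.4–8.5%. With persistent differences between children (about 92% passing by day 28), the ratio is 1.18–1.42 and type I error 10.0–16.6%.

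**Pooled t-test by simulation** (sequences of up to 28 daily SBTs). Type I error was about 6–8% when children's pass chances varied with SD 0.5 logits. At SD 1 to 1.5 logits it ran from about 9% to 28%, depending on pass rate and correlation. In settings near the plan's figures (28–34% passing first time, 7–14% never passing; SD 1.5–2 logits, correlation 0.4–0.8) it was 10–18%, and the slowest 24 children supplied 39–48% of the failed SBTs.

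**Which case is plausible?** If every child had a 25% daily chance of passing, 0.75^28 = 0.03% would remain unpassed at day 28, about 0.1 of 240 children. The plan expects about 24. Death or extubation without a pass may explain part of the gap, but persistent differences between children are the natural reading. The final SAP's change notes describe the same shape: most children passed within three days, while two never passed and were still ventilated at 90 days.

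**The case against.** Four points on the other side carry weight.

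- **Independence is inferred.** A reader might infer that the plan treats daily SBTs as independent. It does not say so. The t-test sentence speaks of patients, and one SBT per child is an open reading that has no clustering error. What stands is that the choice is not stated, while the same paragraph frames the analysis around each SBT.
- **Repeated measures are recognised beyond the multivariable model.** The final SAP's GEE and mixed-model provisions can reasonably be taken to cover the comparison of aPiMax means. They do not supply a variance for an AUC or for a difference between AUCs.
- **Too narrow is not automatic.** The table includes settings with never-passers in which the ordinary test is accurate, and others in which it is conservative.
- **The stakes are limited.** A reader might infer that univariable p-values decide which measures enter the multivariable model. No section says this; the model simply comes next, and it is hierarchical. Ranking by AUC point estimate does not use the standard error either; only the claim that one AUC exceeds another does.

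The calculations also stop at a child's first pass. Section D.3.5 has a child who passes but is not ready for extubation repeat the SBT 24 hours later, so passes can repeat too.

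**Conclusion.** The point holds as a gap with a real consequence for the AUCs. Nothing in the documents gives the chi-squared AUC comparison a clustered variance, and nothing fixes the unit of analysis for the univariable pass/fail tests.

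If all SBTs are pooled with ordinary standard errors, those errors can be off in either direction. For the mean comparison they run from about 30% too large (1/0.77 = 1.30) to about 46% too small (1 − 1/1.86). For the AUC difference they run from about right to about 30% too small (1 − 1/1.42). Type I error is near or below 5% when pass chances are similar or long runs are few, and roughly 10 to 20% when a few children supply long runs of failure; the extreme corner of the table reaches 29%. These sizes rest on an assumed correlation (0.3 to 0.8 across the checks) and an assumed spread of failed SBTs. Only the pass rates come from the plan.

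This concerns a secondary outcome of a secondary aim. The randomised comparison of weaning duration is untouched.

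**What to change.** State in D.6.4.2 and in the SAP which SBTs per child enter, and adopt one of two routes.

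1. **First SBT only** for the pass/fail contrasts, the AUCs and their comparison. About 60 passes and 180 failures, one per child, make the ordinary tests valid. The price is precision: the SE factor for the mean difference is √(1/60 + 1/180) = 0.149, against a correctly computed pooled factor of √0.00640 = 0.080 to √0.01325 = 0.115 in the two worked examples.
2. **All SBTs**, with GEE or a mixed model (child as cluster) for the mean contrasts, which the SAP already allows. For the AUCs and their differences, use a bootstrap that resamples children in place of the ordinary chi-squared test.

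Either route needs no new data and only a little more analysis work. Intervals may widen.

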We will measure patient effort of breathing twice daily with esophageal manometry (using Pressure Rate Product [PRP] and Pressure Time Product [PTP]) and once daily using diaphragm ultrasound (using Diaphragm Contractile Activity [DCA]), during the acute and weaning phases in both arms. DCA is obtained by measuring the thickness of the right hemi-diaphragm and calculating the percent difference between diaphragm thickness on inspiration and exhalation. Diaphragm ultrasound measurements will be performed independently by 2 practitioners, one of whom is specifically trained in acute care ultrasound. We will also use ultrasound to measure diaphragm thickness on exhalation and monitor how this changes serially over time as a measure of the architecture of the diaphragm. Finally, we will measure respiratory load (resistance, compliance) daily using spirometry. The clinical team will remain blinded to the results of these measurements in both arms.

D.4.2. Spontaneous Breathing trial respiratory measurements during Airway Occlusion:

Airway Occlusion: Prior to each SBT, we will perform a standardized airway occlusion maneuver to measure neuromuscular capacity with aPiMax (airway) and ePiMax (esophageal), as described in the Preliminary Data. In addition, during airway occlusion we will measure DCA (as above)^{5, 7, 51, 52}, to provide complementary data to PiMax. The clinical team will remain blinded to the results of these measurements in both arms.

D.4.3 Weaning trial measurements during SBTs:

During SBTs, respiratory effort and capacity will be measured with PRP, PTP, inspiratory pressure from esophageal manometry (Pi), Pi/ePiMax, Tension Time Index (TTI), Phase angle (PA), and DCA. Patients will be monitored continuously during the SBT, and all of these measures will be recorded at the beginning of the SBT, and then every 30 minutes (for 5 minute periods) to monitor respiratory muscle endurance over time. The PRP measurements will be shared with the clinical team in both arms because they will be used to help define passage of SBTs (as above). Clinical providers will remain blinded to the results of the other measurements in both arms.

Data Collection timeline	Enrollment	Acute (Daily)	Weaning (Daily)	SBT	Post-Extubation
Demographics (age, race, gender, past medical history, primary diagnoses, comorbidities, PRISM-III-12 severity of illness scores, height, weight, quality of life score)					

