Clinical Variables (total dose of sedatives, analgesics, highest/lowest/modal sedation scores, pain scores, corticosteroids, aminoglycosides, fluid balance, caloric and protein intake, hypoxemia markers, dead space markers, ventilator type and settings (q6h), blood gasses (all), inotropes/vasopressors, organ failure scores (PELOD), procedures)					
Effort of Breathing and Respiratory Load					
Esophageal Manometry : PRP, PTP, TTI, Pi					
Respiratory Inductance Plethysmography ⁴⁴ : Phase Angle (PA)					
Ultrasound : Diaphragm Contractile Activity (DCA)					
Spirometry : Resistance, Dynamic and Static Compliance					
Respiratory Muscle Strength (during airway occlusion)					
Esophageal Manometry : Esophageal PiMax (ePiMax)					
Airway Pressure : Airway PiMax (aPiMax)					
Ultrasound : DCA during airway occlusion					
Diaphragm Architecture (Thickness on Exhalation)					
Outcomes (Weaning Duration, VFDs and components, reintubation, Non-Invasive Ventilation use and duration, ICU, Hospital, 90-day mortality, quality of life score)					

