D.6.2 Rationale for Randomization Strategy: Age stratified randomization is necessary because *age is an important biological variable* likely to confound the relationship between respiratory muscle weakness and length of weaning. This will ensure an equal age distribution amongst treatment groups. Age groups are based upon accepted pediatric definitions, and have been used in numerous other pediatric RCTs. Neonates (< 1 month) have been excluded because they are often managed with different ventilator strategies and because normal values for PiMax are lower in neonates ^{63, 64}. Immunosuppression is a known risk factor which affects duration of ventilation and weaning, and an imbalance in immunosuppression between groups has been shown to significantly confound previous pediatric mechanical ventilation studies. The additional weaning phase randomization is necessary because we anticipate an imbalance of the number of patients who will be extubated after the acute phase between REDvent-acute and control groups. Acute phase management may have a sustained effect on neuromuscular strength that will affect the duration of weaning. To understand whether the REDvent strategy during the weaning phase can prevent prolonged weaning, risk factors for prolonged weaning (which may be different based on acute phase management) need to be rebalanced with a second randomization. Ultimately, this will allow us to determine the independent utility of REDvent-acute and REDvent-weaning components.

D.6.3 Preparation of the Analysis Data Set

Datasets for analyses consist only of data for which all queries have been resolved. In addition to data management steps to reduce error in data acquisition and entry, a biostatistical cleaning will focus on inconsistencies, missing data and outliers in variables related to the derivation of key outcomes. These activities will be ongoing throughout the study and will involve both the data management team and the biostatistics team.

Preplanned construction of new variables will be conducted in accordance with the study hypotheses and analysis plans. Variable transformation may be required for interpretive

and statistical purposes. With respect to the primary outcome of weaning duration, patients who do not progress to the weaning phase within 28 days (i.e. death, prolonged severe illness) will not be included in analysis of the primary outcome, but will be considered for secondary outcomes.

D.6.4 Statistical Analysis Plan

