Analysis and Sample Size: The primary outcome of this aim is aPiMax < 30 cmH₂O. The analysis will focus on determining whether the degree of patient effort of breathing is independently associated with the development of respiratory muscle weakness. PRP will be the primary measure of effort of breathing, and will be measured twice daily in both acute and weaning phases. Secondary measures of effort of breathing include DCA and PTP. For the acute phase, we will generate a time- weighted average PRP during the acute phase and graph it against aPiMax at the first SBT, anticipating a positive correlation (higher average PRP values associated with higher aPiMax). We will subsequently dichotomize aPiMax at the first SBT and compare mean time weighted average PRP in the acute phase between aPiMax groups (> 30 vs. ≤ 30 cmH₂O). For the weaning phase, we will graph the changes in aPiMax throughout the weaning phase (from first failed SBT until successful SBT) against time-weighted average PRP, with the anticipation that low PRP will be associated with either further reductions in aPiMax, or no improvement, while PRP in the physiologic range of 150-400 will be associated with improvement in aPiMax. We will subsequently dichotomize aPiMax (at 30 cm H₂O) at the time of successful passage of an SBT and compare time-weighted average PRP in the weaning phase between aPiMax groups. Subsequently, we will build a multivariable logistic regression model on the outcome of aPiMax ≤ 30 cmH₂O to determine if time- weighted PRP in the acute phase, weaning phase or both have an independent association with preserving aPiMax, after controlling for confounding variables (data collection table). We anticipate that 35% of patients (at least 80) will have aPiMax ≤ 30 cmH₂O, allowing for inclusion of at least 9 variables in the multivariable model. Secondary goals are to characterize other variables that retain an independent association with low aPiMax, which are likely to include age group, use and dose of neuromuscular blockade, driving pressure during the acute phase of ventilation, sepsis, corticosteroids and use of aminoglycoside antibiotics.

D.6.5 Dissemination plan and data archiving

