28-day ventilator free days (secondary outcome)	Number of days between index intubation and 28-days post-index intubation in which patient is alive and not on IMV.	No exclusions.	Competing risks regression adjusting for blocking variables and confounders. Censoring indicators: 0=those who do not die but are not extubated within 28 days 1=those that have successful liberation within 28-days 2=those that die within 28-days	If patient is re-intubated within 24 hours of extubation the time in between intubations is not counted towards VFDs. If a patient is extubated for >24 hours and then subsequently re-intubated they get credit for those days without IMV. Values are 0 to 28 days. Adjusted hazard ratio and 95% C.I. will be presented.	January 2023- Updated competing risk regression to negative binomial model to align with analysis plan for primary outcome and because the variable is a count of the number of days. Negative binomial also treats death and those on IMV for 28 days as the same (zero VFDs). This aligns with the hypothesis that the influence of the treatment variable is on the days of ventilation, and we do not expect any treatment effect for death.
PiMax on day of 1st SBT (secondary outcome)	PiMax value on the day the 1 st SBT was performed.	Patient with values >100 will be truncated to 100. Exclude patients who never attempted an SBT in the 28-days study period.	Multiple linear regression adjusting for blocking variables and confounders.	Adjusted mean difference with 95% C.I. will be presented for REDvent vs. Usual care.	June 2024- unable to satisfy assumptions of linear regression with any transformation. Modeled as non-parametric proportional odds logistic regression.

PiMax on day of extubation (secondary outcome)	PiMax value on the day of extubation. Restricted to those who met primary outcome (SBT passage or successful extubation).	Patient with values >100 will be truncated to 100. Exclude patients who died within 24 hours of extubation or remained intubated at 90 days.	Multiple linear regression adjusting for blocking variables and confounders.	Adjusted mean difference with 95% C.I. will be presented for REDvent vs. Usual care.	June 2024- unable to satisfy assumptions of linear regression with any transformation. Modeled as non-parametric proportional odds logistic regression.

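### The formal weaning-phase strength analyses do not pre-specify adjustment for aPiMax before the first failed SBT, so weakness already present at entry to weaning may be read as an effect of low weaning effort

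*Combined protocol and SAP*

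**What the plan says.** **Aim 3 (protocol D.6.4.3).** For the weaning phase the plan takes three steps.

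- A plot: "we will graph the changes in aPiMax throughout the weaning phase (from first failed SBT until successful SBT) against time-weighted average PRP".
- A group comparison: children are split at 30 cmH₂O on aPiMax "at the time of successful passage of an SBT and compare time-weighted average PRP in the weaning phase between aPiMax groups". No covariate is mentioned.
- A logistic model for low aPiMax that tests time-weighted PRP from the acute phase, the weaning phase or both, "after controlling for confounding variables (data collection table". The table meant is the data collection timeline in D.4.3. It is long and includes aPiMax, but no covariate is singled out.

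**Availability of the baseline (D.4.2).** "Prior to each SBT, we will perform a standardized airway occlusion maneuver to measure neuromuscular capacity". The first such value precedes the failed SBT that triggers weaning randomisation (D.3.4).

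**Carry-over (D.6.2).** "Acute phase management may have a sustained effect on neuromuscular strength that will affect the duration of weaning".

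**Randomised comparison (final SAP, July 2024).** Table 1 lists this secondary outcome: "PiMax value on the day of extubation. Restricted to those who met primary outcome (SBT passage or successful extubation". On the blocking variables used for adjustment, the SAP states: "For the weaning phase this is acute phase randomization grouping and age group". The May 2024 section names oxygenation index as the confounder for PiMax and replaces linear regression with proportional odds. An earlier PiMax value could enter only if it were treated as a weaning-phase baseline variable and found imbalanced.

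**The concern.** Aim 3 asks whether effort is independently associated with the development of weakness. Splitting on aPiMax at SBT passage measures weakness present at that moment, whether it developed during weaning or was there at the start. PRP is derived from esophageal pressure swings, so a weak child may also generate less PRP during weaning. If so, low weaning PRP and low final aPiMax would go together even if weaning effort did nothing. The plan's own premise in D.6.2, that acute management may leave a lasting mark on strength, makes the first-SBT value the obvious common cause to control.

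The mechanistic conclusion about weaning effort is at stake. For the randomised PiMax comparison the issue is different and smaller: leaving out a strong prognostic baseline costs power in an otherwise unbiased analysis.

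**Working it through.** **1. The plan's own figure.** Low-aPiMax patients: 0.35 × 240 = 84, which matches the 84 given for Aim 2 and satisfies the at least 80 given for Aim 3. Nine variables imply 80/9 = 8.9 to 84/9 = 9.3 events each. The base of 240 includes children who pass the first SBT (about 25% in D.6.4.1).

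**2. Events in the weaning phase.** D.6.4.1 expects 180 children there. Applying the same 35%, 0.35 × 180 = 63 events. That supports 63/10 = 6.3 to 63/8.9 = 7.1 variables, not 9.

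**3. False-positive rate of the unadjusted Aim 3 comparison.** Inputs: n = 180 and 35% low (plan); two-sided 5% (SAP). Assumed, because the documents do not give them: ρ, the correlation of first-SBT with final aPiMax; and r, the correlation of first-SBT aPiMax with weaning PRP. The true effect of weaning PRP is set to zero.

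With no direct effect, corr(final aPiMax, PRP) = ρr. Splitting a normal variable at 35% multiplies the correlation by φ(−0.385)/√(0.35 × 0.65) = 0.777. With q = 0.777ρr, the t-test has noncentrality q√180/√(1 − q²). For ρ = 0.5 and r = 0.3, q = 0.1165, the noncentrality is 1.57 and rejection is 35%. Simulation with 10,000 trials per cell:

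| ρ | r | Unadjusted rejection | Closed form | Adjusted for first-SBT aPiMax |
|---|---|---|---|---|
| 0.5 | 0 | 4.8% | 5% | 5.2% |
| 0.5 | 0.1 | 7.5% | 8% | 5.1% |
| 0.5 | 0.2 | 19% | 18% | 5.3% |
| 0.5 | 0.3 | 34.5% | 35% | 4.9% |
| 0.7 | 0 | 5.3% | 5% | 4.8% |
| 0.7 | 0.1 | 11% | 11% | 5.5% |
| 0.7 | 0.2 | 31% | 31% | 5.2% |
| 0.7 | 0.3 | 59% | 60% | 5.2% |

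A separate simulation put the ρ = 0.5, r = 0.3 cell at 33%, hence the range 33–35%.

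**4. Does the change plot remove the problem?** With no true effect, corr(change, PRP) = −r√((1 − ρ)/2). At ρ = 0.5, r = 0.2 this is −0.10; at ρ = 0.7, r = 0.3 it is −0.12. The plot is biased in the opposite direction, so two steps of the same paragraph could point different ways. It is also only a graph.

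**5. Randomised PiMax at extubation, 90 per arm, illustrative 0.4 SD effect.** Under proportional odds the standard error of the log-odds ratio does not shrink: about 0.26–0.27 without the baseline and 0.27–0.28 with it, because the adjusted effect is larger on that scale. Power rises from about 0.78 to 0.87 (ρ = 0.5) or 0.97 (ρ = 0.7). The normal-theory benchmark, with residual SD √(1 − ρ²), gives 0.77, 0.87 and 0.96. A check with six ordered categories (900 trials per cell) gave 0.72, 0.82 and 0.93. The level depends on the coding, but the gain is about 10 to 20 percentage points each way.

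**The case against.** The plan does not overlook first-SBT strength. It is the starting point of the Aim 3 change plot, a predictor of weaning duration in Aim 2 and a secondary outcome in the SAP. The logistic model may draw on a table that contains aPiMax, and it can include acute-phase PRP. The randomised comparison already adjusts for acute group, age group and oxygenation index, which absorb part of the carry-over. All of this stands, so a reader who infers that the plan ignores baseline strength goes too far. What is missing is a commitment to adjust for it in the formal analyses.

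The drugs and conditions listed at the end of D.6.4.3 might be read as the model's covariates. They are given as predictors expected to emerge under secondary goals, so their failure to include aPiMax proves nothing.

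The size of the bias rests on assumed correlations. Pressure support in REDvent-weaning is titrated to a PRP range, which should weaken the link with strength in that arm. PRP also includes respiratory rate, so even the sign of r is not certain; a negative r would still inflate a two-sided test. The rates in the table apply to the unadjusted comparison, not to a multivariable model that happened to include first-SBT aPiMax.

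A reader might also expect a 13–29% smaller standard error in the randomised comparison, from √(1 − ρ²) at ρ = 0.5 to 0.7. That belongs to the linear model that the final SAP replaced. Nor do the documents support calling that comparison biased, and no calculation here supports adding the covariate to the length-of-weaning analysis.

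**Conclusion.** The concern holds as a gap in pre-specification. The unadjusted Aim 3 weaning comparison may attribute to weaning effort a weakness that was present before weaning began. Under the assumed correlations (r 0.1 to 0.3), its false-positive rate is about 8% to 33–35% at ρ = 0.5 and 11% to 59% at ρ = 0.7. It is the nominal 5% if first-SBT strength and weaning PRP are unrelated. The documents do not show that confounding will occur, only that the plan leaves it uncontrolled although the variable is collected.

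For REDvent-weaning versus usual care, the omission costs power and not validity. The estimates assume 90 per arm and an illustrative 0.4 SD effect, with ρ taken as the correlation left after the covariates already in the model.

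**What to change.** **Protocol D.6.4.3.** Fit a separate weaning-phase model, restricted to children who failed the first SBT. Regress aPiMax at SBT passage on time-weighted weaning PRP, with continuous pre-first-SBT aPiMax as a covariate. Base the conclusion about weaning effort on this model, and keep the unadjusted comparison and the change plot as description. If the outcome stays dichotomised, plan for 6 to 7 variables.

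Two limits apply. Do not add this covariate to the joint logistic model, or to any analysis estimating the effect of acute-phase PRP or of REDvent-acute, because first-SBT strength lies on that pathway and adjusting would remove the effect sought. Do not include first-SBT passers: their value before the first SBT and their value at passage are the same measurement, so the outcome would be its own covariate.

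**Final SAP, Table 1.** For REDvent-weaning versus usual care, add pre-first-SBT aPiMax to the proportional-odds model for PiMax on the day of extubation. Label it a sensitivity analysis, since the unblinded statistician had already begun model checking by May 2024.

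**Cost.** One covariate, no new measurement, and the loss or imputation of a few children without a first-SBT value.
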